9.3.3 Validity and Reliability

The data collected for this study will be recorded in eCRF from routine clinical practice for the documentation and decision-making for a patient's care and through validated questionnaires.

9.4 Data Sources

Specific eCRFs will be designed to collect all the variables needed for this long-term follow-up study. The data in the baseline and follow-up period will be collected through patient questionnaires to be populated by the patient's parents (guardian)/paediatrician (as appropriate) and through medical chart review. Data abstraction from medical chart review will be performed approximately every 6 months (± 30 days) from enrolment. Additional data on neuropsychomotor development will be assessed through specific questionnaires (paper and/or electronic) which will be administered at pre-specified intervals starting at enrolment (approximately every 6 months [± 30 days] for patients up to 6 years old and approximately yearly [± 60 days] for patients from 6 years old) either in person or via telephone interview or mail.

9.5 Study Size

The targeted sample size for this study is approximately 298 patients. However, the actual number of patients that will be included in the study will depend on the results of site feasibility, willingness of patients (or their legal guardians/caregivers) or sites to participate in the study.

According to Marshall et al 2013, paediatric ALL patients are expected to have toxicity during intensification of therapy, generally related to hematological counts (Marshall et al, 2013). All patients also expect to have some immune complications after treatment end (Perkins et al, 2017) that will persist for some time.

Assuming that between 85%-98% of all patients will have at least one event, the expected ranges of sample sizes and relevant 95% CI is provided below. If 100 patients are enrolled.

95% C	onfidence	Interval o	of Estimated	Incidence o	of Adverse	Events by	Sample
-------	-----------	------------	--------------	-------------	------------	-----------	--------

S	ize	

Enrolled N Per Arm	Estimated Incidence of events	95% Confidence Interval*
150	98%	94.3%-99.3%
150	90%	84.1%-93.9%
150	85%	78.4%-89.8%
100	98%	93%-99.5%
100	90%	82.5%-94.5%
100	85%	76.7%-90.7%
75	98%	90.8%-99.3%
75	90%	82.0%-95.4%
75	85%	75.6%-91.6%
50	98%	89.5%-99.7%
50	90%	78.6%-95.7%
50	85%	71.5%-91.7%

* Wilson score interval

Sample size calculation for comparison analyses was calculated based on the number of long-term survivors needed. A risk difference of 10% (98% vs 88%) is considered as clinically significant. If the sample size is 52 long-term survivors per arm (104 in total), then a risk difference of as little as 10% will be detectable (p-value < 0.05).

Number of Long-term Survivors per Arm	Observed Risk Difference	P-value*
52/52	98% vs 88% = 10%	0.0455
40/40	98% vs 86% = 12%	0.0477
30/30	98% vs 83% = 15%	0.0477
20/20	98% vs 77% = 21%	0.0444

* z-test of two proportion comparison

Assuming a 35% long-term survival rate, the required number of patients entering the study per arm is 149 (52/0.35). Therefore, the number of patients entering the study needed to successfully fulfill the primary objectives while taking into account the 35% survival rate is 298.

Even though long-term survivors contribute the most essential data to this study, all enrolled patients contribute important information. If the total sample size is 149 patients per arm (298 in total), then a risk difference of as little as 5% will be detectable (p-value < 0.05).

Enrolled N per Arm	Observed Risk Difference	P-value*
149/149	98% vs 95% = 5%	0.0375

* z-test of two proportion comparison

It will be attempted to recruit an approximately equal number of patients for each age group of long-term survivors (0-2 years, 3-6 years, 7-12 years, 13-17 years) to ensure that there will be enough data collected for each age group.

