7.3 Statistical Inference

The study will compare blinatumomab therapy versus chemotherapy for the occurrence of neuropsychomotor developmental impairment, neurological impairment, endocrine impairment, and immune system impairment.

8. Research Question and Objectives

The overarching aim of this study is to describe and compare the long-term safety profile of B-precursor ALL paediatric patients who have been treated with either blinatumomab or chemotherapy prior to undergoing alloHSCT.

Primary 8.1

Primary Objective					
Objective	Endpoint				
 To estimate incidence of neuropsychomotor developmental impairment, endocrine impairment, neurological impairment, and immune system impairment (including auto-immune disorders and vaccine failure) 	 Impairment defined as any of the following: Neuropsychomotor development impairment in any area of social and emotional, language/communication, cognitive, or motor Neurologic impairment defined as any peripheral nervous system disorders including neuromuscular junction disorders; central nervous system disorders Endocrine impairment defined as any Hypothalamus-Pituitary-Gonadal Axis disorders; Hypothalamus-Pituitary-Adrenal (HPA) Axis disorders; Hypothalamus-Pituitary-Thyroid Axis disorders Immune system impairment defined as any leukopenia (neutropenia and/or lymphopenia); low IgG; low IgM, and; low IgA; autoimmune disorders; vaccination failure 				

8.2	Secondary
•	

• To estimate the incidence of Haemopoietic Stem Cell Transplant (HSCT) related adverse events (AEs)	 HSCT-related AEs defined as any second malignancy; Graft versus Host Disease (GvHD); infection, and/or; relapse
 To estimate the incidence of subsequent relapse of leukemia including in the central nervous system (CNS) 	 Relapse is defined as any of the following: Isolated bone marrow relapse (M3³ in the absence of extramedullary involvement) Combined bone marrow response (M2 or M3 marrow and at any extramedullary manifestation of ALL) Extramedullary relapse (either CNS relapse, testicular relapse, or relapse at other sites⁴)

³ Cytological bone marrow assessment grading: see Appendix F for details
 ⁴ See Appendix F for relapse criteria (including extramedullary relapse)

 To estimate the cumulative incidence of long-term AEs 	 AEs in any of the following organ systems: gastrointestinal, hematologic, dermatology, cardiac, pulmonary, hepatic, renal, neurological, infection, immunology, and skeletal

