9.7.2.2.3 Analysis of the Primary and Secondary Endpoints

Patient incidence proportions (and 95% Cls) for each of the specified outcome events will be summarized. KM estimates for time to first onset of each specified event will be provided.

For the events of interest, events that occur after a relapse or secondary malignancy will be censored as it is unlikely that events that occur after relapsed and treatment for relapse could be considered related to initial chemotherapy or blinatumomab treatment for the prior disease occurrence.

A comparison between the blinatumomab versus chemotherapy group will be conducted at the final follow-up in the study pending adequate sample size is enrolled $(\geq 50 \text{ patients per arm})$ and the blinatumomab and SOC groups are comparable (eg. there is overlap between PS distributions across the two groups, or no critical differences that cannot be accounted/adjusted for). Prior to comparison being conducted, covariates listed in Section 9.3.2 will be evaluated for differences between the two groups. Any covariates that are not comparable between the two (Wald chi-square or t-test, p-value < 0.25), will be evaluated as a covariate for adjustment in the models. The primary and secondary endpoint of discrete events (eg, incidence endpoints) will be compared by a logistic regression which will generate an odds ratio and 95% confidence interval of the odds of developing an event. Endpoints that are time-to-event will be compared by a Cox regression model which will generate hazard ratio and 95% confidence interval for the risk of developing an event. Also, we will additionally conduct a propensity score weighting analysis based on the covariates collected for this study. An additional sensitivity analysis may be done to adjust for the drop-in effect of patients receiving anti-cancer medications during follow-up.

A literature review of published data at the time of the final study report will be performed for the relevant endpoints. If there is any relevant scientific data publicly available by the time when the study ends (> 12 years later), Amgen will provide a comparative analysis. If a sufficient number of patients are identified in publicly available database with information on relevant confounding factors, Amgen will conduct a direct comparative analysis, but descriptive analyses will be undertaken either way.

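### The 10- and 5-point detectable differences in Section 9.5 hold only when event rates are near 0% or 100%, yet they are stated without limit for a comparison of four separate impairments

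*Protocol*

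**What the plan says.** Section 9.5 assumes one event rate: "Assuming that between 85%-98% of all patients will have at least one event". Two supports are given. The first is that "paediatric ALL patients are expected to have toxicity during intensification of therapy, generally related to hematological counts". The second is that "All patients also expect to have some immune complications after treatment end".

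For the comparison, "A risk difference of 10% (98% vs 88%) is considered as clinically significant". The section continues: "If the sample size is 52 long-term survivors per arm (104 in total), then a risk difference of as little as 10"% will be detectable at p < 0.05. Dividing 52 by a 35% long-term survival rate gives 149 per arm. The protocol concludes that the "number of patients entering the study needed to successfully fulfill the primary objectives while taking into account the 35% survival rate is 298". It adds that with all 149 per arm a difference as small as 5 points is detectable.

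Section 7.3 states what is compared: "The study will compare blinatumomab therapy versus chemotherapy for the occurrence of neuropsychomotor developmental impairment, neurological impairment, endocrine impairment, and immune system impairment". Section 9.7.2.2.3 says that incidence proportions with 95% CIs "for each of the specified outcome events will be summarized". Sections 8.1 and 9.3.1, however, introduce the primary endpoint as impairment in any one of the four domains.

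**The concern.** The precision of a proportion, and of a difference between two proportions, depends on where the rates lie. Near 98% the binomial variance is close to its minimum, so a difference that just reaches significance there can fall well short at 30% or 50%. The sizing uses only the near-ceiling rate, while the planned comparison names four impairments. Both supports for the rate concern blood counts or immunity. The first also concerns therapy given before follow-up starts, since Section 9.2.1 sets day 1 at completion of the transplant. Nothing in Section 9.5 speaks to neuropsychomotor, neurological or endocrine rates.

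Section 7.2 names neurological and endocrine effects among the gaps that motivate the study. A reader who relies on Section 9.5 would expect a 10-point difference in either to be detectable among survivors, and would expect 298 patients to suffice for all four domains.

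**Working it through.** **Inputs from Section 9.5.** 52 survivors per arm; 149 enrolled per arm; contrast 98% vs 88%; 35% survival; z-test of two proportions. In that section detectable means that the observed difference gives p < 0.05; no power is stated.

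**Formulas.** With p̄ the mean of the two rates, n per arm and d the difference:
- s0 = √(2·p̄(1−p̄)/n), z = d/s0, two-sided p.
- Power = Φ((d − 1.96·s0)/s1), where s1 = √((p1(1−p1) + p2(1−p2))/n).

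**Reproducing the plan.** For 98% vs 88% at n = 52, p̄ = 0.93, s0 = √(2 × 0.93 × 0.07/52) = 0.0500, z = 0.10/0.0500 = 2.00 and p = 0.0457 (printed 0.0455). 52/0.35 = 148.6, so 149 per arm and 298 in total. For 149 per arm, 98% vs 93% gives p = 0.0374 (printed 0.0375). The row is printed as 98% vs 95%, which is a 3-point difference and gives p = 0.159. The 95% looks like a slip for 93%, and I take 93% as intended.

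**Inside the protocol's own range.**
- 85% vs 95% at n = 52: s0 = √(2 × 0.90 × 0.10/52) = 0.0588, z = 1.70, p = 0.089.
- 85% vs 90% at n = 149: s0 = √(2 × 0.875 × 0.125/149) = 0.0383, z = 1.30, p = 0.19.

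These two results need no assumption from outside the document.

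**Where the stated differences hold.** On a grid of whole percentages, 10 points at 52 per arm reaches p < 0.05 only if the lower rate is at most 2% or at least 88%. Five points at 149 per arm does so only if the lower rate is at most 2% or at least 93%.

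**Assumed rates for single impairments.** The protocol gives none, so the lower rates below are assumptions.

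| Lower rate | 10 points, n = 52: p (power) | 5 points, n = 149: p | Smallest significant observed difference, n = 52 / n = 149 (points) | True difference with 80% power, n = 52 / n = 149 (points) |
|---|---|---|---|---|
| 5% | 0.089 (40%) | 0.10 | 12.1 / 6.2 | 19.2 / 9.7 |
| 10% | 0.153 (30%) | 0.19 | 14.6 / 7.9 | 22.2 / 11.9 |
| 20% | 0.239 (22%) | 0.30 | 17.4 / 9.9 | 25.5 / 14.4 |
| 30% | 0.285 (19%) | 0.36 | 18.8 / 10.9 | 27.0 / 15.7 |
| 40% | 0.305 (17%) | 0.38 | 19.3 / 11.4 | 27.1 / 16.2 |
| 50% | 0.305 (17%) | 0.39 | 18.9 / 11.3 | 26.3 / 16.0 |

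By the same formula, power for the plan's own contrast of 98% vs 88% at 52 per arm is 52%, because its p-value sits just under 0.05.

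**The case against.** The strongest reply is that the sizing matches a composite endpoint. Sections 8.1 and 9.3.1 define impairment as any of the listed domains, and a rate of patients with at least one event fits that wording. The immune domain alone counts any leukopenia, low immunoglobulin, autoimmune disorder or vaccination failure, so it could plausibly lie in the 85%-98% range. This stands as far as it goes: the text allows a composite reading. It does not settle the matter. Section 7.3 still promises a comparison of the four impairments, and the stated differences fail within 85%-98% as well.

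Second, the 10 points are called clinically significant for 98% vs 88% specifically, not as a margin at every base rate. That is correct, and it is a reason to limit the statement to that contrast.

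Third, the primary objective is estimation. The comparison is conditional on at least 50 patients per arm and comparable groups, and results come as odds or hazard ratios with 95% CIs that would show imprecision. This stands too. A reader might infer that the plan sets up a non-significant neurological or endocrine result as proof of safety; the protocol plans no such conclusion.

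A reader might also infer that the rate rests only on treatment-phase blood counts. It does not, because post-treatment immune complications are cited next.

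**Conclusion.** As written, the detectable-difference statements are too general, and the claim that 298 meets the primary objectives is not supported for each impairment. The failure inside 85%-98% (p = 0.089 and 0.19) rests on the protocol's figures alone. The wider results rest on assumed lower rates of 10%-50%, on the pooled z-test, and on 52 and 149 per arm. They give 15-19 points instead of 10, and 8-11 points instead of 5, as the smallest significant observed difference.

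Three stronger readings are not supported.
- That 298 is miscalculated: 52, 149 and 298 all reproduce from the stated inputs.
- That the stated differences fail for all four impairments: no component rates are given, immune impairment may be near the ceiling, and a very rare impairment meets the criterion by symmetry (2% vs 12% at 52 per arm, p = 0.046; 2% vs 7% at 149 per arm, p = 0.037).
- That the study cannot show a 10-point difference at mid-range rates: power is low, at about 17%-30% among survivors, but not zero.

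This is a correction to what Section 9.5 claims. It does not show that the design has failed.

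**What to change.** In Section 9.5:
1. State whether the sizing refers to the composite of any impairment or to each impairment.
2. Limit the 10-point statement (52 per arm) and the 5-point statement (149 per arm) to contrasts with one rate at about 98%.
3. Add rows for the separate impairments at rates labelled as assumed, for example 5%, 10%, 20%, 30% and 50%. Give Wilson 95% CIs, as in the existing table, and the true difference with 80% power. From lower rates of 10%-50% that difference is about 22-27 points at 52 per arm and 12-16 points at 149 per arm.
4. Replace the statement that 298 is what the primary objectives need with the precision delivered for each domain.

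Keep the target of 298. The cost is some wording and a small table, with no extra patients and no change to the analysis. The downside is that the stated figures become less favourable.

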9.1 Study Design

This is a prospective, multi-country, multi-center observational study involving long-term follow-up of B-precursor ALL patients treated with either blinatumomab or SOC chemotherapy prior to alloHSCT. The study will have no effect on treatment practices of included patients due to its observational nature. The primary and secondary objectives relate to the description and comparison (pending adequate sample size is enrolled [≥ 50 patients per arm]) of the long-term safety profile of blinatumomab versus chemotherapy, prior to alloHSCT, in paediatric patients.

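### Section 9.5 calls differences detectable when the planned numbers give only about 52-56% power for them, and the 149-per-arm row is wrong as printed

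*Protocol*

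**What the plan says.** Section 9.5 sets the target effect: "A risk difference of 10% (98% vs 88%) is considered as clinically significant". For 52 survivors in each arm, 104 altogether, the section concludes: "then a risk difference of as little as 10% will be detectable (p-value < 0.05"). The support is a table whose columns are the number of survivors per arm, the "Observed Risk Difference" and a p-value, footnoted as a "z-test of two proportion comparison". Its rows are 52 per arm (98% vs 88%, p=0.0455), 40 (98% vs 86%, p=0.0477), 30 (98% vs 83%, p=0.0477) and 20 (98% vs 77%, p=0.0444). No power is stated anywhere in the section.

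The enrolment target follows: "Assuming a 35% long-term survival rate, the required number of patients entering the study per arm is 149 (52/0.35"). Doubled, this is 298, described as the number needed to fulfil the primary objectives.

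For all enrolled patients, the section says that with 149 per arm, "then a risk difference of as little as 5% will be detectable". The supporting row pairs 98% vs 95% with a difference of 5% and p=0.0375.

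Sections 9.1, 9.7.2 and 9.7.2.2.3 make the comparison conditional, "pending adequate sample size is enrolled", on at least 50 patients per arm. Section 9.7.2.2.3 also requires the groups to be comparable.

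**The concern.** In a sample-size section, a detectable difference is normally one that the study would find with a stated, high probability if it existed. Here the term means that a result exactly equal to that difference would just pass p<0.05. An estimate falls above or below the true value about equally often. A sample size at which the true difference sits on the significance boundary therefore has about even odds of a significant result.

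This matters because 52 is the number from which 149 and 298 are derived, and because the study is a post-authorisation safety study. The error to fear is a missed harm. A reader told that 10 points was detectable may give a non-significant comparison more weight than it can bear. Separately, the 149-per-arm row contradicts itself, since its two rates differ by 3 points and not 5.

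**Working it through.** **Inputs (Section 9.5).** The rates and numbers per arm are as tabulated. The significance level is 0.05, which must be two-sided because the printed p-values reproduce only that way. Long-term survival is 35%. Power is not stated, so 80% below is a conventional benchmark and an assumption.

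**1. Reproduce the survivor table.** Pooled z-test without continuity correction: z = |p1 − p2| / SE0, with SE0 = √[2p̄(1 − p̄)/n].

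For 52 per arm, p̄ = 0.93, SE0 = √(2 × 0.93 × 0.07/52) = 0.0500, z = 0.10/0.0500 = 1.998 and p = 0.0457.

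| n per arm | Rates | p recomputed | p printed |
|---|---|---|---|
| 52 | 98% vs 88% | 0.0457 | 0.0455 |
| 40 | 98% vs 86% | 0.0479 | 0.0477 |
| 30 | 98% vs 83% | 0.0476 | 0.0477 |
| 20 | 98% vs 77% | 0.0446 | 0.0444 |

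With z rounded to two decimals (2.00, 1.98, 1.98, 2.01), all four printed values match exactly. The table therefore treats the rates as observed results.

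**2. Power if those rates are true.** Power = Φ[(d − 1.96 × SE0)/SE1], with SE1 = √{[p1(1 − p1) + p2(1 − p2)]/n}.

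For 52 per arm, SE1 = √[(0.0196 + 0.1056)/52] = 0.0491. Then (0.10 − 1.96 × 0.0500)/0.0491 = 0.04, and Φ = 51.6%. Exact binomial enumeration of the same z-test gives 53.1%. The other three rows give 50.7%, 50.9% and 52.0% by the normal formula.

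**3. The inflation step.** 52/0.35 = 148.6, rounded up to 149, and 2 × 149 = 298. This is correct.

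**4. The 149-per-arm row.**

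| Rates | Difference | z | p | Power, normal | Power, exact |
|---|---|---|---|---|---|
| 98% vs 95% (as printed) | 3 points | 1.41 | 0.159 | 29.0% | 27.7% |
| 98% vs 93% | 5 points | 2.08 | 0.0374 | 54.9% | 56.5% |

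Pooled or unpooled, with or without continuity correction, one- or two-sided, 98% vs 95% gives p between 0.079 and 0.274, never 0.0375. With z rounded to 2.08, 98% vs 93% gives exactly 0.0375.

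**5. What the planned numbers deliver at 80% power, starting from 98%.**

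| n per arm | Normal formula | Exact enumeration |
|---|---|---|
| 52 | about 16.5 points | about 15 points |
| 149 | about 7.6 points | about 7 points |

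For scale, 80% power for 98% vs 88% needs 102 survivors per arm by the normal formula, and 102/0.35 = 291.4, or 292 enrolled per arm.

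**6. The trigger of 50 enrolled per arm.** If all 50 per arm are analysed, power for 98% vs 88% is 50% (normal) or 51% (exact). If only long-term survivors were analysed, 50 × 0.35 = 17.5, or 17-18 per arm, and power would be 20-21% (normal) or 10-12% (exact).

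**The case against.** The section discloses its method. The columns are labelled as observed differences and p-values, and no power figure is claimed. The primary objective in Section 8.1 is to estimate incidence, and it is supported by a separate table of Wilson intervals that this point does not touch. Sections 9.7.2 and 9.7.2.2.3 report odds or hazard ratios with 95% confidence intervals and set no decision rule based on significance. The comparison will be covariate-adjusted or propensity-weighted, so unadjusted power figures are approximations.

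All of this stands, and it limits the point without removing it. Sections 7.3, 8 and 9.1 state that the arms will be compared, and Section 9.5 rests 298 on that comparison.

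Four stronger readings are tempting, and the protocol supports none of them:

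- A reader might infer that 298 rests on the faulty 149 row. It does not; it follows from 52/0.35.
- A reader might infer that the study must grow to about 292 per arm. That figure assumes 80% power, which the protocol never sets as a requirement.
- A reader might infer that the trigger releases a comparison with only 10-21% power. That holds only for a survivors-only analysis. Section 9.7.2 tabulates the total eligible population, Section 9.7.2.2.3 does not restrict the comparison to survivors, and Section 9.5 sizes an all-enrolled comparison separately. The trigger is also not the only condition, and a minimum for fitting a model need not equal the target size.
- A reader might infer that the protocol plans to treat a non-significant result as reassurance. It does not say so.

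**Conclusion.** The point holds. The differences called detectable are those at which an observed result just reaches p<0.05. If they are true, power is about 52-53% for 10 points with 52 survivors per arm, and about 55-56% for 98% vs 93% with 149 per arm. The 149 row is wrong as printed: its rates differ by 3 points, with p=0.159 and power of about 28-29%. Its stated difference and p-value agree with each other only at 98% vs 93%, which suggests a one-digit slip.

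These figures assume a two-sided 0.05 level, equal arms, an event rate of 98% in one arm and an unadjusted z-test. The weakness lies in the comparative justification of the sample size. The confidence-interval table and the division by 0.35 are not affected by it.

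**What to change.** Keep the sample size and revise Section 9.5 as follows:

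- Replace the statements of detectability with the power delivered. For 52 survivors per arm, state about 50% power for 10 points and 80% power for about 15-16.5 points (exact to normal formula). For 149 per arm, state about 55% power for 98% vs 93% and 80% power for about 7-7.6 points. Label 80% as a conventional benchmark.
- Reconcile the 149-per-arm row, whose difference and p-value fit 98% vs 93%.
- State that a non-significant comparison does not exclude a 10-point difference.
- Leave the trigger of at least 50 enrolled per arm unchanged. Add a note that if the comparison were restricted to long-term survivors, 50 enrolled would leave about 17-18 per arm at 35% survival, with about 10-21% power for 10 points.

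The cost is rewording and a less favourable stated detectable difference. No patients are added and no analysis changes. Raising the trigger to full target enrolment is not proposed: it would change the analysis plan, because any shortfall in one arm would then cancel the comparison or reduce it to description.
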